
The CGI is shown below:

1. Severity of illness

Considering your total clinical experience with this particular population, how mentally ill is the patient at this time?

- 0 = Not assessed
- 1 = Normal, not at all ill
- 2 = Borderline mentally ill
- 3 = Mildly ill
- 4 = Moderately ill
- 5 = Markedly ill
- 6 = Severely ill
- 7 = Among the most extremely ill patients

2. Global improvement: Rate total improvement whether or not, in your judgment, it is due entirely to drug treatment.

Compared to his condition at admission to the project, how much has he changed?

- 0 = Not assessed
- 1 = Very much improved
- 2 = Much improved
- 3 = Minimally improved
- 4 = No change
- 5 = Minimally worse
- 6 = Much worse
- 7 = Very much worse

3. Efficacy index: Rate this item on the basis of **treatment effect only**.

Select the terms which best describe the degrees of therapeutic effect and side effects and record the number in the box where the two items intersect.

EXAMPLE: Therapeutic effect is rated as 'Moderate' and side effects are judged 'Do not significantly interfere with patient's functioning'.

Therapeutic effect		Side effects			
		None	Do not significantly interfere with patient's functioning	Significantly interferes with patient's functioning	Outweighs therapeutic effect
Marked	Vast improvement. Complete or nearly complete remission of all symptoms	01	02	03	04
Moderate	Decided improvement. Partial remission of symptoms	05	06	07	08
Minimal	Slight improvement which doesn't alter status of care of patient	09	10	11	12
Unchanged or worse	Not assessed = 00	13	14	15	16

STUDY PROCEDURE PROTOCOL

PRE-TREATMENT ACTIVITIES

STUDY QUALIFICATION

SIGNING OF INFORMED CONSENT FORM

The PI will commence by presenting and reviewing in detail the items in the informed consent form with the individual's designated caregiver(s) and answer any questions he or she may have. To proceed, the individual's designated caregiver must willingly sign the informed consent form.

ASSIGNMENT OF SUBJECT IDENTIFICATION NUMBER

The subject will be assigned a unique subject identification number based upon his or her order of entry into the study.

Additional information about the informed consent and subject ID number assignment is contained in a later section of the protocol titled, "SAFETY AND CONFIDENTIALITY ISSUES."

SUBJECT GROUP RANDOMIZATION

Subjects will be randomly assigned to either Treatment Group A or to Treatment Group B, following the methodology outlined above in the STUDY DESIGN section of the protocol.

STUDY QUALIFICATION EVALUATION: INCLUSION/EXCLUSION CRITERIA

The following tools from the Study Test Battery to be used during Study Qualification Evaluation

- Diagnostic and Statistical Manual of Mental Disorders, 4th Edition, Text Revision criteria (DSM-IV-TR)BDI®-II
- Autism Diagnostic Interview (ADI-R)
- Aberrant Behavior Checklist (ABC) Irritability Subscale
- Clinical Global Impressions – Severity (CGI-S) scale

INCLUSION CRITERIA

- Male or female child or adolescent aged 5 to 17 years
- Subject has met Diagnostic and Statistical Manual of Mental Disorders, 4th Edition, Text Revision criteria (DSM-IV-TR) for autistic disorder within the past 2 years, as diagnosed by a trained, qualified medical professional such as a pediatric neurologist, child psychiatrist or developmental pediatrician
- Diagnosis is confirmed by Autism Diagnostic Interview (ADI-R)
- Subject demonstrates 'irritable' behaviors such as tantrums, aggression, self-injurious behavior, or a combination of such behaviors
- Subject's Aberrant Behavior Checklist (ABC) Irritability Subscale score is ≥ 18
- Subject's Clinical Global Impressions – Severity (CGI-S) scale score is ≥ 4 (4=moderately ill)
- Subject's current therapeutic/intervention plan for treating his or her autistic disorder (educational/behavioral or other therapy; medication use; dietary interventions) has been consistent/stable over at least the past 3 months

- Subject's caregiver agrees, and it is possible for, the subject to abstain from partaking in new treatments to treat the subject's autistic disorder symptoms during the course of participation in the study. This includes educational/behavioral therapy, dietary interventions, medications such as FDA-approved Risperdal® and Abilify® and other medications often prescribed for the treatment of other autism-related symptoms, such as anxiety, depression, or obsessive-compulsive disorder, including antipsychotic medications used to treat severe behavioral problem, and medications used to treat people with attention deficit disorder
- Female subjects of child-bearing age are willing and able to use acceptable means of contraception throughout study participation. Acceptable means of contraception throughout study participation are: oral contraceptives (birth control pills); injectable contraceptives (such as Depo-Provera, Noristeret and Lunelle); vaginal ring (e.g. Nuva Ring); birth control patch (e.g. Ortho Evra); cervical diaphragms, caps and sponges; male or female condoms; Intrauterine Devices (IUDs); Intrauterine Systems (e.g. Mirena); sterilization and abstinence.

EXCLUSION CRITERIA

- Subject has primary or concurrent diagnosis of another disorder or other identifiable genetic condition associated with the autism spectrum scale or with mental retardation, including:
 - ✓ PDD-NOS
 - ✓ Asperger's Disorder
 - ✓ Rett's Disorder
 - ✓ Fragile-X Syndrome
 - ✓ Childhood Disintegrative Disorder
 - ✓ Down Syndrome
- Seizure disorders (active), cerebrovascular disease or brain trauma as etiology of autistic behavior
- Current diagnosis of, and treatment for, bipolar disorder, psychosis, schizophrenia, or major depression
- Current use of a psychotropic drug deemed effective for the treatment of aggression, tantrums or self-injurious behavior
- known neurological disease, such as encephalitis
- significant sensory or motor impairment such as cerebral palsy
- diagnosis of epilepsy that is currently treated with anti-convulsant medication
- Previous significant head trauma
- Hearing loss requiring use of assistive devices such as hearing aids or cochlear implant
- Significant visual impairment that cannot be adequately corrected with lenses
- Documented mental age younger than 18 months
- HIV and other autoimmune disorders
- Active cancer or treatment for cancer within last 6 months
- Unstable cardiac disease, such as a recent cardiac arrhythmia (including atrial fibrillation, ventricular fibrillation and irregular atrial-ventricular conduction time), or recent congestive heart failure, or recent myocardial infarction
- Previous surgical interventions to the head/neck area
- Sensitivity to, or contraindication for, light therapy
- Subject is presently pregnant or breast feeding
- Participation in a research study within the past 30 days

BASELINE ASSESSMENT

DEMOGRAPHICS AND TREATMENT HISTORY

(i) Demographic Variables

The following demographic variables will be recorded for each subject:

1. *Gender*: male or female.
2. *Age*
3. *Ethnicity*: Caucasian, Hispanic, African American, American Indian, Asian/Pacific Islander, Other.

(ii) Medication and Treatment History

A list of the following information about a subject's current and past medication and therapy use will be recorded:

- ✓ All prescription and OTC medications used to date to treat the subject's symptoms of autistic disorder. Include information on daily dosage and duration of use, as applicable:
 - Current medications
 - Non-current medications
- ✓ All therapies (conventional and alternative) used to date to treat the subject's symptoms of autistic disorder. Include information on frequency and duration of application, as applicable:
 - Current therapies
 - Non-current therapies
- ✓ All current medications (prescription and OTC) and therapies (conventional and alternative) currently used for non-autism disorder related indications. Include information on medication dosages and duration of use and frequency and duration of therapy applications, as applicable, as well as the indications for which each is being used.

BASELINE EVALUATION

The following tools from the Study Test Battery to be used during Study Baseline Assessment:

- Aberrant Behavior Checklist (ABC)
- Clinical Global Impressions (CGI) Severity of Illness Scale (CGI-S) only

PROCEDURE ADMINISTRATION PHASE

GENERAL ASSESSMENT CONDITIONS

- Subjects will be required to maintain their regular medication and dosage schedule used to treat symptoms related to autism disorder throughout the study. **Subjects will not be required to stop taking any medications used to treat their autism disorder symptoms or for any other indication, as already prescribed by a treating physician, throughout the duration of participation in the study.**
- Subjects must agree to not change or start taking any new medications, or partake in any other new treatments, or to change the dosages they take of current medications, to treat the symptoms of autism disorder, during the course of study participation.
- Subjects must agree to notify the study investigator immediately if their treating physician makes any change to medication or dosage.
- Females of child-bearing age must agree to use acceptable means of contraception, as detailed in the study qualification evaluation section.

STUDY TREATMENT ADMINISTRATION PROTOCOL

- The study treatment administration phase will extend over four consecutive weeks.
- Each subject will receive a total of eight study treatments with the Erchonia® HLS laser device, two treatments per week for 4 consecutive weeks, each treatment administration 3 to 4 days apart.
- Each study treatment will be administered by the study investigator at the study test site.
- Each study treatment administration will last 5 minutes.

Erchonia® HLS Treatment Administration Protocol

The treatment administration process is as follows:

1. The subject is seated comfortably.
2. The administration investigator puts on the KenTek Corporation KenTek C22-KMT-6101 light blue safety glasses.
3. The subject is correctly fitted with the KenTek Corporation KGOG-6101 light blue Medium Goggles safety goggles.
4. The Erchonia® HLS laser is applied four inches from the skin surface, and the laser light is directed perpendicular to the plain of the skin ensuring that the beam is penetrating perpendicular to the skin.
5. Pulsed laser therapy 8, 53, 73 and 101 is applied systematically to the base of the brain and temporal areas for 5 continuous minutes.
6. The HLS laser is turned off.
7. The administration investigator removes the safety glasses and the subject removes the safety goggles.
8. The treatment session is complete.

STUDY EVALUATION TIMELINE

The study evaluation phase is as follows:

- ✓ Treatment Administration Phase: 4 weeks
- ✓ Post-treatment Evaluation Phase:
 - 4 weeks for all subjects
 - 6 months for subjects who had been assigned to the active treatment group

The evaluation time points and associated measures to be evaluated during the course of this study are as follows:

TREATMENT ADMINISTRATION PHASE: 4 WEEKS

At Each of the 8 Study Treatment Administration Visits

- Medication and therapy use review
- Adverse events evaluation

WEEK 2 END: Study Midpoint

Following completion of the first 2 weeks of the Treatment Administration Phase (after the 1st 4 treatments), the following study measures will be recorded:

- Aberrant Behavior Checklist (ABC)
- Clinical Global Impressions (CGI)

WEEK 4 END: Study Endpoint

Following completion of the 4-week Treatment Administration Phase (after completion of all 8 treatment administrations), the following study measures will be recorded:

- Aberrant Behavior Checklist (ABC)
- Clinical Global Impressions (CGI)

POST-TREATMENT EVALUATION PHASE

WEEK 8: All Subjects

Four weeks following completion of the 4-week Treatment Administration Phase (8 weeks after study onset), the following study measures will be recorded:

- Aberrant Behavior Checklist (ABC)
- Clinical Global Impressions (CGI)
- Medication and therapy use review
- Adverse events evaluation

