5. An individual for whom the caregiver decides not to permit participation in the study will continue to work with the physician on the ASD treatment plan goals for the minor patient.

Compensation

A subject or his or her caregiver(s) will not be offered money or any other form of compensation to participate in the clinical study; however, there will also not be any charge for the cost of the study treatments with the Erchonia® HLS laser device or for the cost of any other directly-related evaluations or measurements that occur as part of the subject's participation in this study.

Subject Sample Size

There will be 40 qualified subjects enrolled in this clinical study:

- 20 subjects in the test group
- 20 subjects in the control group

Rationale and Justification for Sample Size

This study is powered to compare one active arm with placebo. Sample size calculation is based on the primary efficacy measure of the mean change from study baseline to endpoint (end of the 4-week treatment period) in the Aberrant Behavior Checklist (ABC) Irritability Subscale score adjusted for the baseline ABC Irritability Subscale score.

Based on detecting a mean difference of -8.5 points between test and placebo groups in the change in ABC Irritability Subscale score adjusted for the baseline ABC Irritability Subscale score being considered clinically relevant with a SD of 8.9, a two-sided test with 80% power and a 5% level of significance, the number of subjects needed per treatment group is 18.

From here, it is anticipated that about one-tenth of subjects overall may withdraw or be terminated from the study prior to completion for various reasons. Therefore, the following formula is used to determine the final needed starting sample size for each procedure arm:

Final sample size = sample size X $1/(1-d)$; where $d = \# \text{ expected dropouts}/\# \text{ subjects enrolled}$.

Final sample size = $18 \times 1/(1-0.11)$; where $d = 2/19$

Final sample size = $18 \times 1/0.89 = 18 \times 1.124 = 20$ subjects per treatment group.

Therefore, a minimum starting sample size of 20 subjects in each treatment group (40 subjects in total) is needed to ensure that a sufficient number remains at study endpoint (18 evaluable subjects per treatment group) for any significant differences found between treatment groups to be considered statistically valid and representative of the general population being sampled.

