- Mean change from baseline to endpoint in the other 4 ABC Subscale scores, based on ratings by the subject's primary caregiver:
 - ✓ Lethargy/Social Withdrawal
 - ✓ Stereotypic Behavior
 - ✓ Hyperactivity/Noncompliance
 - ✓ Inappropriate Speech
- Mean change from baseline to endpoint in the global ABC score
- Change in ratings on the CGI-S from baseline to study endpoint evaluation
- Change in ratings on the CGI-I from baseline to study endpoint evaluation

STATISTICAL METHODS

Efficacy analysis will be according to the intent to treat (ITT) principle by last observation carried forward (LOCF).

Intent to Treat: Subjects will be included in the ITT analysis if they complete their baseline clinical assessments and had at least one post-randomization efficacy evaluation and corresponding baseline value.

Last observation carried forward (LOCF): Missing data will be handled by carrying forward the last observation for the relevant measure. The LOCF data set included data recorded at a given time point, or, if no observation was recorded at that time point, data carried forward from the previous time point with available data. Baseline data will not be carried forward or averaged to impute missing values for the LOCF data set.

STATISTICAL ANALYSIS

Primary Efficacy Analysis

For the continuous primary efficacy measure of ABC Irritability Subscale score, change scores will be evaluated by analysis of covariance (ANCOVA). The ANCOVA models for LOCF data sets will include the baseline measure as a covariate and treatment (active of placebo) as main effects.

Secondary Measures Analysis

- For the continuous secondary efficacy measures of the other 4 ABC Subscale scores, and the Global Score, change scores will be evaluated by analysis of covariance (ANCOVA). The ANCOVA models for LOCF data sets will include the baseline measure as a covariate and treatment (active of placebo) as main effects. A two-way significance level of 5% will be considered to be statistically significant.

- For the categorical measures of the CGI will be analyzed within the framework of the generalized Cochran-Mantel Haenszel (CMH) procedure.
- Responder rate will be evaluated using Fisher's exact test to compare the proportion of responder rates between the test and control groups.

P-values will be 2-tailed tests of significance rounded to 3 decimal places. All analyses will be performed at the 5% significance level.

SAFETY ANALYSES

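### The Week 2 and Week 4 assessments are worded as following completed treatments, and nothing provides for scoring a child who misses or stops sessions, although the deciding analysis is called ITT.

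*Combined protocol and SAP*

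**What the plan says.** Two sets of statements bear on when the primary score is taken.

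- **Tied to treatments received.** Under Study Evaluation Timeline, the Week 4 entry reads "Following completion of the 4-week Treatment Administration Phase (after completion of all 8 treatment administrations), the following study measures will be recorded". The Week 2 entry has the same form, with the first four treatments in place of all eight.
- **Tied to the calendar.** The same entries are headed as the ends of Weeks 2 and 4. Primary Efficacy Outcome Measure places the endpoint at the close of the four-week treatment period. The Table of Subject Events lists the Week 2 and Week 4 measures with no condition on treatments received.

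The Week 8 entry differs. It is headed for all subjects and is timed as "Four weeks following completion of the 4-week Treatment Administration Phase (8 weeks after study onset", with no count of treatments.

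For the analysis, Statistical Methods says "Efficacy analysis will be according to the intent to treat (ITT) principle", using last observation carried forward (LOCF). A child enters the ITT set with a baseline value and at least one efficacy evaluation after randomisation. Baseline values are not carried forward. The opening of the Statistical Analysis Plan makes this ITT LOCF analysis the one that decides success.

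The documents give no visit window, no assessment for a child who stops early, and no statement that a child with fewer than eight treatments is or is not scored at Week 4.

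**The concern.** An ITT analysis compares the randomised groups whatever treatment was received, so it needs the outcome at the stated time from children who did not finish the course. A site applying the Week 4 entry literally would take no score from a child who had five, six or seven sessions, even if the caregiver were willing to complete the form. An obtainable observation would become a missing one, and LOCF would then put the mid-course score in its place. Under the Week 2 wording, a child who stopped after three sessions would have no score to carry.

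This is separate from whether LOCF is a good way to fill a gap. The visit wording decides whether the gap exists. If children miss sessions for reasons linked to tolerance or lack of benefit, which is plausible but not documented, the loss is not random, and the collected data could not show its direction.

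**Working it through.** **1. Timing for a child on schedule.** Eight sessions 3 to 4 days apart make seven gaps, so the last falls 7 × 3 = 21 to 7 × 4 = 28 days after the first. The fourth falls 3 × 3 = 9 to 3 × 4 = 12 days after the first. The two kinds of wording therefore agree for a child on schedule and diverge only for one who misses or stops sessions.

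**2. What the text does with an off-schedule child, read literally.**

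- *Stops after the Week 2 score:* no observed Week 4 score; the Week 2 value is carried forward.
- *Stops before the Week 2 score and is not seen again:* no post-baseline score, so outside the ITT set.
- *Stops before the Week 2 score but is seen at Week 8:* meets the ITT entry condition, yet has no Week 4 value, because values are carried forward in time only.

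**3. The plan's own sample size.** Inputs, from Rationale and Justification for Sample Size: "Based on detecting a mean difference of -8.5 points between test and placebo groups in the change in ABC Irritability Subscale score"; "with a SD of 8.9, a two-sided test with 80% power and a 5% level of significance"; result "the number of subjects needed per treatment group is 18".

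- n per arm = 2 × [(1.960 + 0.842) × 8.9 / 8.5]² = 17.2, rounded up to 18. This reproduces the plan. The t-based solution is 18.2, or 19.
- Inflation: 18 / 0.89 = 20.2, stated as 20; with 10% dropout, 18 / 0.90 = 20 exactly.

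**4. Children lost before Week 2.** Normal-approximation power = Φ(δ / (SD × √(2/n)) − 1.960). For n = 20, the standard error is 8.9 × √(2/20) = 2.81, so power = Φ(8.5/2.81 − 1.960) = 85.5%. The plan expects that "about one-tenth of subjects overall may withdraw or be terminated from the study prior to completion for various reasons", and one-tenth of 20 is 2 per arm. The n = 20 row assumes that children who stop keep the full 8.5-point effect.

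| Per arm in analysis | Normal | t-based |
|---|---|---|
| 20 (all scored) | 85.5% | 83.7% |
| 18 (2 lost) | 81.7% | 79.5% |
| 16 (4 lost) | 77.1% | 74.3% |

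**5. Children carried forward from Week 2.** Let d be the fraction of each arm carried forward and f the share of the Week 4 effect already present at Week 2. The documents do not give f, so its full range is shown. Expected difference = 8.5 × (1 − d + d × f), with n = 20 per arm.

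| d | f | Difference | Normal | t-based |
|---|---|---|---|---|
| 0.10 | 0 | 7.65 | 77.6% | 75.5% |
| 0.10 | 0.5 | 8.08 | 81.8% | 79.8% |
| 0.10 | 1 | 8.50 | 85.5% | 83.7% |
| 0.20 | 0 | 6.80 | 67.6% | 65.3% |
| 0.20 | 0.5 | 7.65 | 77.6% | 75.5% |
| 0.20 | 1 | 8.50 | 85.5% | 83.7% |

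The d = 0.20 rows and the 4-lost row double the plan's attrition to show sensitivity.

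**The case against.** The strongest reply is that the parenthetical only describes sequence: score the child after the last scheduled session. The calendar headings, the endpoint definition and the unconditional Table of Subject Events support that reading. This stands in part. There is no express bar on scoring a partly treated child, and the literal reading is an inference from the wording plus silence. But the documents leave both readings open on the primary endpoint and give a site nothing to settle the choice.

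The size is also open to challenge, and these points stand:

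- The one-tenth figure counts children who withdraw or are terminated from the study. Some would be unreachable under any visit rule, and children who stay but miss a session are not in it.
- The sample size already allows for losing 2 per arm, and by the normal approximation 18 per arm still gives 81.7%.
- A child who stops may gain nothing further. The Week 2 and Week 4 scores would then agree, and collecting the second would change little.
- Where effect would still have accrued in active children, carrying Week 2 forward shrinks the difference, which works against the device.

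A reader might infer three stronger points that the documents do not support:

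- *That Week 8 also depends on finishing eight treatments.* It is for all subjects and carries a calendar time. Its two time references can separate if sessions slip, but Week 8 does not enter the primary analysis.
- *That the sample size section treats stopping treatment as leaving the study.* It speaks only of leaving the study and is silent on children off treatment but still followed.
- *That 4 of 40 children will lack a Week 4 score because of this rule.* No such count is given.

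**Conclusion.** The point holds for Weeks 2 and 4. The assessment wording depends on treatments completed, the endpoint and the ITT label do not, and no provision reconciles them for a child who misses or stops sessions. Taken literally, the wording gives up primary data that could be had from a short caregiver form.

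The effect on power is probably modest. At 2 per arm, loss before Week 2 costs about 4 percentage points (t-based 83.7% to 79.5%), and carry-forward costs between 0 and about 8 points (normal 85.5% down to 77.6%). These figures rest on the plan's 8.5-point difference and SD of 8.9, on children who stop keeping the full effect in the reference case, and on an assumed Week 2 share of the effect. They illustrate what is at stake if all the expected leavers could have been scored; they do not estimate what the fix would recover. The larger reason to act is that the missingness may depend on outcome in a trial of 20 per arm. The change should be made, but the point does not by itself undermine the design.

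**What to change.** In the Week 2 and Week 4 entries of the Study Evaluation Timeline, and in the Table of Subject Events, state that the ABC and CGI are collected at the end of calendar Weeks 2 and 4, each with a stated window. Collect them in every randomised child who passes qualification, regardless of the number of treatments received, unless consent for data collection is withdrawn. Count time from the first treatment, or from the baseline visit if a qualified child is never treated. The restriction to qualified children is needed because the protocol places randomisation before the qualification evaluation, so some randomised children may prove ineligible and never be treated. In Statistical Methods, state that observed Week 4 scores are used in the primary ITT analysis whether or not the child was still on treatment.

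The cost is protocol wording and a few extra visits or caregiver forms; the protocol puts the ABC at 10 to 15 minutes. The downside is that some scores will be observed off treatment, which may modestly dilute the estimated difference.
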